 - < 70 mg/dl
 - 70-120 mg/dl
 - 70-180 mg/dl
 - >180 mg/dl
 - >250 mg/dl
- Within day coefficient of variation (CV)
- Mean postprandial excursion (difference in CGMG from the beginning of the meal challenge to the peak CGMG in the 4 hours after the meal) for both mixed meal challenges
- Number of symptomatic hypoglycemic events per day
- Grams of carbohydrate consumed to treat hypoglycemia per day
- TDD of insulin

VI. b. 3. Other Outcomes

- Mean number of meal announcements per day
- CGM Reliability index, calculated as percent of possible values actually recorded by CGM
- CGM MARD from Dexcom G5 CGM versus time-stamped BG values from meter downloads (any other BG values will not be considered)
- Percentage of days with mean CGM glucose < 154 mg/dl (estimated average glucose corresponding to

an A1c of 7%)

- Mean postprandial AUC (4 hours following each meal challenge) for both mixed meal challenges
- Mean number of daily BG measurements
- Number of severe hypoglycemic events (subject unable to self-treat, requiring the assistance of another person)
- Mean daily basal insulin dose
- Mean daily bolus insulin dose
- List of technical faults associated with the bionic pancreas including cause and resolution

The primary analysis of the designated endpoints will be calculated on an intention-to-treat basis. In cases where an arm was not completed we will use the available data from that arm in the data analysis. We will calculate percentages, means standard deviations (and medians and interquartile ranges as appropriate), and ranges in descriptive analyses. We will use paired t-test for comparison of means for normally distributed outcomes and the Wilcoxon Signed Rank test for comparisons of medians on non-normally distributed outcomes. In a secondary analysis we will look for any period effect and any interaction between treatment and period, although no such interaction is predicted and there is probably insufficient power to identify a small interaction. We may, in exploratory analyses, also stratify subjects for secondary analyses of the pre-specified endpoints by the following characteristics: sex, age, usual care insulin total daily dose, body mass index, baseline A1c, and use of CGM in usual care.

VI. c. Power Analysis

As this study is exploratory in nature, no formal power analysis has been performed. From our insulin specific data collected in our previous study, we identified 7 out of 22 had a difference in t_{max} , 6 out of 22 had a difference in $t_{1/2max}$ and 14 out of 22 had a difference in terminal half-life. We'd like to recruit all 22 of these subjects to participate in this study. Given the occurrence rate of different PK profiles, we believe this will still capture significant information. The sample size of 4 for the Test Run period is a convenience sample with no statistical implications.

We previously showed in a multicenter, outpatient, random-order crossover trial (n=39, 11 days each arm) that the bionic pancreas (BP) reduced group mean CGM glucose (141 ± 10 vs. 162 ± 29 mg/dl, $p < 0.0001$) and percent of time spent <60 mg/dl (0.6 ± 0.6 vs. $1.9 \pm 1.7\%$, $p < 0.0001$) relative to usual care (UC) with pump \pm CGM (El-Khatib FH, et al. Lancet. 2017; 389:369–80). We applied a statistical approach to these data that we will use in this study for comparisons within subjects to determine how many individuals saw benefit for each outcome. We compared the average CGM glucose and average time <60 mg/dl between the BP and UC arms for each patient using autoregressive time series models to determine significance of differences. We found that 72% of subjects had a statistically significant reduction in mean CGM glucose, 51% had significant reduction in time <60 mg/dl, 44% had a significant reduction in both, and 97% had a significant reduction in at least one outcome. These analyses provide a new prospective on the efficacy of the BP emphasizing the benefit to individuals rather than the group as a whole. Subjects least likely to benefit were those who had extremely tight glycemic control and minimal hypoglycemia under UC.

VII. Risks and Discomforts

Subjects may experience mild discomfort associated with the insertion of the infusion set and the Dexcom sensor into the SC tissues. This is expected to be the same as their usual care.

There is a risk of hypoglycemia. This risk is expected to be less than the risk during the subjects' lives outside the trial based on data from earlier trials. All of our previous studies have shown that hypoglycemia is significantly reduced in all configurations of the bionic pancreas when compared with usual care. Based on our experience,

we believe that the risk of hypoglycemia will be less than or equal to the risks that they are exposed to on a daily basis while living with type 1 diabetes outside of the trial.

Even though no increase in hypoglycemia was observed in subjects with T1D using BC222 inuslin lispro under MDI or open-loop regimen, there may be an increased risk of hypoglycemia with the ultra-rapid BC222 insulin lispro, which is expected to have a faster onset than rapid acting analogs. Subjects will be trained on the recognition and treatment of hypoglycemia, and the risk of using an ultra-rapid insulin will be explained to them. We anticipate the bionic pancreas will adapt to the faster pharmacokinetic profile of BC222 insulin lispro, and that hypoglycemia will not be higher than what the insulin-only bionic pancreas is able to achieve with rapid-acting insulin. We believe that the risk of hypoglycemia is further mitigated by keeping the PK parameter settings of the iLet at 65 minutes, despite the possibility BC222 is faster than that. The Test Run period using BC222 lispro in the iLet in a supervised setting will be completed and reviewed for safety prior to initiating any outpatient experiments using BC222 lispro.

There is a risk of hyperglycemia. This risk is expected to be similar to or less than the risk during the subjects' lives outside of the trial based on data from earlier trials in subjects with type 1 diabetes.

VIII. Potential Benefits

Based on evidence from previous trials of the bionic pancreas and the design of this trial, subjects enrolled in the study may benefit from a reduction in risk of hypoglycemia and hyperglycemia and a better mean glucose than they typically achieve.

Subjects are expected to benefit in all arms of the study from the formal involvement of a designated contact who will serve as a backup to respond to any overnight threshold alarms to which the subject does not respond.

The data obtained may be used to improve diabetes care, and the bionic pancreas, by identifying the advantages of individualizing insulin use based on a personalized PK profile. If participants are able to easily identify a type of insulin that can optimize their glycemic control, they could have better outcomes regardless of their insulin delivery method. This study is a necessary step in making individualized insulin prescriptions based on PK parameters a reality. In addition, this study will provide useful data in preparing the bionic pancreas to become available to people with type 1 diabetes. Wide availability of the bionic pancreas could improve the care in adults and children with diabetes.

Subjects will be financially compensated for participating in the study.

IX. Data and Safety Monitoring

IX. a. Monitoring of Source Data

During the experiment, Dexcom CGM data will be collected in various ways. Dexcom CGM data, calibration data, and insulin dosing data will be automatically stored in the bionic pancreas device (from which it will be downloaded at intervals) and wirelessly streamed to the cloud where it will be stored to provide redundancy in data storage and mitigate the risk of data loss. All of the data will be combined in a single database that will be compared against the primary data files for integrity. The computer database will be backed up at least monthly and the backup media stored in a secure location.

Study staff will be encouraged to raise any concerns they may have or problems they have identified at any time. The PI, in consultation with the co-investigators, will decide a course of corrective action, and resolution or progress will be assessed no later than the next meeting.

An audit of procedures, regulatory documentation, and a sample of subject files will be performed by a member of the Diabetes Research Center at least biannually. The audit will be conducted by a staff member who is not

directly involved in the conduct of the study. This audit will include a review of regulatory documentation, such as IRB and FDA correspondence, and a review of subject files, including a review of consents, case report forms, and other data from study visits.

A numeric code will be substituted for the subject's personal identifying information in the study database, which will be password protected. The key linking the medical record number of the subject with the numeric code, along with case report forms, and all information that is personally identifiable, will be kept in a locked filing cabinet in an investigator's locked office. All electronic records will be kept in a password protected computer database. All printed computer data will be disposed of confidentially when no longer needed. Only the study staff will have access to the study database. Subjects may not withdraw from the de-identified database, but they may elect to have the key linking their medical record to the de-identified database destroyed.

The study data may be shared with collaborators at Beta Bionics and Adocia but only in a form in which all personally identifiable information has been removed (e.g. combined database including BG values, CGM values, and record of insulin delivered by the device). Shared data will be in the form of a database in which only a number identifies subjects.

Subjects may not withdraw their data, as it will be stored in non-personally identifiable form.

IX. b. Safety Monitoring

This study is considered moderate risk. An external Data and Safety Monitoring Board will oversee the conduct of the study and review its results on a regular basis. The DSMB will be responsible for overseeing the transition from the Test Run period to the RCT portion of the study. They will be informed of any events described in the stopping criteria below that occur in the Test Run period. If there are no events for DSMB review, then the RCT portion of the study will be initiated prior to their review of the data.

Additionally, the DSMB will be informed in the event of any severe or unexpected adverse events in the RCT portion of the study. The DSMB will have unblinded access to the drug assignments to assess whether adverse events are associated with insulin administration. The DSMB will be informed if there are any changes to the study protocol that could significantly impact the safety or scientific validity of the study. A final DSMB meeting will convene after the completion of the study. Safety and efficacy data will also be reported to the FDA in compliance with applicable regulations.

The participation of individual subjects will be discontinued if they experience:

- Subjects experience one episode of diabetic ketoacidosis (DKA) requiring hospitalization
 - Hyperglycemic events will be classified as DKA if the following are present:
 - Symptoms including but not limited to polyuria, polydipsia, nausea or vomiting
 - Serum ketones $> 1.5 \text{ mmol/L}$ or large/moderate urine ketones
 - Either arterial blood pH < 7.30 or venous pH < 7.24 , or serum bicarbonate < 15
 - Treatment provided in a healthcare facility
- Subjects experience one episode of severe hypoglycemia, defined as requiring the assistance of another person due to altered consciousness, and required another person to actively administer carbohydrate, glucagon or other resuscitative actions. This means the participant was impaired cognitively to the point that he/she was unable to treat himself/herself, was unable to verbalize his/her needs, was incoherent, disoriented, and/or combative, or experienced seizure or coma. If plasma glucose measurements are not available during such an event, neurological recovery attributable to the restoration of plasma glucose to normal is sufficient evidence that the event was induced by a low plasma glucose concentration.
- The investigator believes it is unsafe for the participant to continue in the study
- A participant becomes pregnant

- The participant requests that the study be stopped

If more than 1 subject must be withdrawn from the study for DKA requiring hospitalization or seizure or unconsciousness associated with hypoglycemia the study will stop and a vote of the DSMB will be required to restart it. All serious and unexpected events will be reported to the DSMB within 72 hours.

Note that subjects may discontinue participation at any time and subjects may be removed from the trial for other reasons, for instance failure to comply with study procedures or concurrent illness that is unrelated to the bionic pancreas but that precludes safe participation. Discontinuation of participation for these reasons will not contribute to a decision to discontinue the trial.

IX. c. Adverse Event Definitions and Reporting Guidelines

Definitions

An **adverse event** is defined as any untoward or unfavorable medical occurrence in a human subject including any abnormal sign (for example, abnormal physical exam or laboratory finding), symptom, or disease, temporally associated with the subject's participation in the research, whether or not considered related to the subject's participation in the research (modified from the definition of adverse events in the 1996 International Conference on Harmonization E-6 Guidelines for Good Clinical Practice).

Hypoglycemic events are recorded as Adverse Events (severe hypoglycemic event) if the event required assistance of another person due to altered consciousness, and required another person to actively administer carbohydrate, glucagon, or other resuscitative actions. This means that the participant was impaired cognitively to the point that he/she was unable to treat himself/herself, was unable to verbalize his/ her needs, was incoherent, disoriented, and/or combative, or experienced seizure or coma. These episodes may be associated with sufficient neuroglycopenia to induce seizure or coma. If plasma glucose measurements are not available during such an event, neurological recovery attributable to the restoration of plasma glucose to normal is considered sufficient evidence that the event was induced by a low plasma glucose concentration.

Hyperglycemic events are recorded as Adverse Events (severe hyperglycemic event) if the event involved DKA, as defined by the Diabetes Control and Complications Trial (DCCT) and described below, or in the absence of DKA if evaluation or treatment was obtained at a health care provider facility for an acute event involving hyperglycemia or ketosis.

Hyperglycemic events are classified as DKA if the following are present:

- Symptoms such as polyuria, polydipsia, nausea, or vomiting;
- Serum ketones >1.5 mmol/L or large/moderate urine ketones;
- Either arterial blood pH <7.30 or venous pH <7.24 or serum bicarbonate <15 ; and
- Treatment provided in a health care facility

The PI and co-investigators will review any adverse events after each experiment to determine severity (serious or non-serious), expectedness (expected or unexpected) and relatedness (related, possibly related or unrelated). The study investigator will assess the relationship of any adverse event to be related or unrelated by determining if there is a reasonable possibility that the adverse event may have been caused by the study intervention.

To ensure consistency of adverse event causality assessments, investigators should apply the following general guideline when determining whether an adverse event is related:

Related: There is a plausible temporal relationship between the onset of the adverse event and the study intervention, and the adverse event cannot be readily explained by the participant's clinical state, intercurrent illness, or concomitant therapies; and/or the adverse event follows a known pattern of response to the study

intervention; and/or the adverse event abates or resolves upon discontinuation of the study intervention or dose reduction and, if applicable, reappears upon re-challenge.

Possibly Related: Possibly related to the research means there is a reasonable possibility that the adverse event, incident, experience or outcome may have been caused by the procedures involved in the research (modified from the definition of associated with use of the drug in FDA regulations at 21 CFR 312.32(a)). Reasonable possibility means that the event is more likely than not related to participation in the research or, in other words, there is a >50% likelihood that the event is related to the research procedures

Not Related: Evidence exists that the adverse event has an etiology other than the study intervention (e.g., preexisting medical condition, underlying disease, intercurrent illness, or concomitant medication); and/or the adverse event has no plausible temporal relationship to study intervention.

Serious adverse event means any event temporally associated with the subject's participation in research that meets any of the following criteria:

- results in death
- is life threatening (places the subject at immediate risk of death from the event as it occurred)
- requires inpatient hospitalization or prolongation of existing hospitalization; • results in a persistent or significant disability/incapacity
- results in a congenital anomaly/birth defect
- any other adverse event that, based upon appropriate medical judgment, may jeopardize the subject's health and may require medical or surgical intervention to prevent one of the outcomes listed above (examples of such events include allergic bronchospasm requiring intensive treatment in the emergency room or at home, blood dyscrasias or convulsions that do not result in inpatient hospitalization, or the development of drug dependency or drug abuse).

Reporting Guidelines

Any serious adverse events or unexpected but related or possibly related adverse events will be communicated to the PI as soon as possible and within 48 hours of the time they are detected. Adverse events will be reported promptly to the Partner's IRB and to the BU IRB. Collaborator [name] is the sponsor of the Investigational Device Exception (IDE) for the bionic pancreas to be used in this trial. Adocia is the sponsor for the Investigational New Drug (IND) application for BC222 insulin lispro to be used in this trial. Reports of adverse events will be made to the FDA in compliance with the terms of IDE and IND.

X. Subject Compensation

Financial compensation will be provided to all subjects who complete the screening visit. Subjects will be paid \$25 for completing the screening visit whether or not they are eligible to participate in the study.

Test Run participants will be compensated \$50 per day. The total compensation for a subject who completed the Test Run would be \$175. Parking expenses will be paid for up to \$30 per subject per day. Subjects who are unable to complete the Test Run or choose to stop participation will receive prorated compensation for the portion of the study visits that they complete. Test Run designated contacts will be compensated \$50 to complete the screening/consent visit. They will be compensated \$50 for completing the study. The total compensation for a Test Run designated contact would be \$100.

Study participants will be compensated \$50 for completing each study visit. Thus the total compensation for a subject who completed the study would be \$225. Parking expenses will be paid for up to \$30 per subject for each visit. Subjects who are unable to complete the study or chose to stop participation will receive prorated

compensation for the portion of the study visits that they complete. Designated contacts for subjects will be compensated \$50 to complete the screening/consent visit. They will be compensated \$50 for completing the study. Thus, the total compensation for a designated contact would be \$100.

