In addition to the iLet itself, the entire iLet BP system includes a glass insulin cartridge, a glass glucagon cartridge, pigtail adapters that connect the drug cartridges to infusion sets, and a self-monitored blood-glucose (SMBG) meter. The SMBG meter that we will use is the Contour Next One (Ascensia). This meter is the successor to the Contour Next SMBG meter (Bayer), which was found to be the most accurate meter assessed in all three blood-glucose ranges tested (< 70, from 70 to 179, and ≥ 180 mg/dl) in a comparative accuracy study involving 17 point-of-care glucose meters.

I. e. Rationale and Potential Benefits

It has generally been assumed that the PK characteristics of rapid-acting insulin analogs are equivalent. This has led to them being treated as a commodity by insurance companies, who generally have only one rapid-acting analog on formulary. However, it is clear from our data that in many individuals there are differences between the PK of insulin lispro and insulin aspart that are consistent across 3 different experiments on different days. If these differences in PK affect glycemic regulation, then better glycemic control may be achieved by identifying a preferred insulin analog for an individual. To determine this, we will test lispro and aspart in the context of the bionic pancreas. We will further examine the effect of PK differences on glycemic control using the experimental ultra-rapid BC222 insulin lispro in a third bionic pancreas study arm, without altering the default PK parameters. An uncontrolled Test Run period with 4 subjects using the iLet with BC222 lispro for three days will be completed prior to initiating outpatient use of BC222 lispro in the iLet to verify safety and feasibility. Data from this Test Run will be reviewed before the RCT period can begin.

II. Hypothesis and Specific Aims

We hypothesize that differences in the PK characteristics of rapid and ultra-rapid insulin analogs will lead to differences in glycemic outcomes when delivered by the *insulin-only* configuration of the bionic pancreas. Specifically, we predict that insulin analogs that have faster absorption (numerically lower T_{max} and/or $T_{1/2max}$) and insulin analogs that have faster clearance (numerically lower terminal half-life) will result in lower mean glucose and/or a lower percentage of time in the hypoglycemic range.

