Aim 1: To conduct a randomized, single-blinded, cross-over study testing the *insulin-only* bionic pancreas in a home-use setting in up to 30 adult subjects (≥ 18 years of age) with type 1 diabetes comparing two commercially available rapid acting insulin analogs, insulin lispro (Humalog, Lilly) and insulin aspart (Novolog, Novo Nordisk.) A final insulin-only bionic pancreas arm will use the experimental ultra-rapid insulin BC222 insulin lispro (BC Lispro, Adocia). The focus will be on determining which fast-acting insulin would be best for use in the iLet bionic pancreas system.

Up to 30 subjects will participate in three 7-day study arms using insulin lispro, insulin aspart, and BC222 lispro in the bionic pancreas in random order. The co-primary outcomes will be mean CGMG and fraction of time spent with CGMG <54 mg/dl with comparisons made between arms for individual participants. Secondary analyses will include time in glycemic ranges (<50 , <60 , <70 , $70-120$, $70-180$, >180 , >250 mg/dl), coefficient of variation, mean postprandial excursion (difference in CGMG from the time of meal announcement to the peak CGMG in the first 4 hours after the meal announcement) for both mixed meal challenges, number of symptomatic hypoglycemic events, grams of carbohydrate consumed to treat hypoglycemia, and TDD of insulin, between arms for individual subjects.

III. Subject Selection

III. a. Inclusion Criteria

1. Age ≥ 18 years and have had clinical type 1 diabetes for at least one year
2. Diabetes managed using an insulin pump for ≥ 6 months
3. Have used a CGM for at least one cumulative month over the last 12 months
4. Prescription medication regimen stable for > 1 month, including any adjunctive anti-diabetic medications (except for medications that will not affect the safety of the study and are not expected to affect any outcome of the study, in the judgment of the principal investigator)
5. Willing to remain within a 250-mile radius of MGH. No air travel will be allowed, and subjects will still be expected to follow the visit schedule as described.
6. Willing to wear one Dexcom CGM sensor, and one leur-lock compatible infusion set that must be replaced every other day
7. Have a mobile phone they will have access to at all times during the study for making contact with study staff

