 19. Electrically powered implants (e.g. cochlear implants, neurostimulators) that might be susceptible to RF interference

20. Unable to completely avoid acetaminophen for duration of study
21. Established history of allergy or severe reaction to adhesive or tape that must be used in the study
22. History of eating disorder within the last 2 years, such as anorexia, bulimia, or diabulenia or omission of insulin to manipulate weight
23. History of intentional, inappropriate administration of insulin leading to severe hypoglycemia requiring treatment
24. Any diagnosed allergy to insulin lispro or insulin aspart
25. Lives in or frequents areas with poor Verizon wireless network coverage (which would prevent study staff from contacting subjects)
26. Any factors that, in the opinion of the principal investigator would interfere with the safe completion of the study

III. c. Source of Subjects

Subjects will be primarily recruited from those who completed our previously conducted Multiplex Pharmacokinetic Study (HRC protocol number 2010P001005), measuring the individual PK profile of each subject for each of the three rapid acting insulins. We will recruit up to 15 subjects who exhibited an atypical PK profile, with the largest differences between the insulin lispro and insulin aspart in either Tmax, T½max, or terminal half-life. Additionally, we will recruit up to 15 subjects who did not have a significant difference in Tmax, T½max, or terminal half-life between insulin lispro and insulin aspart. Most of these subjects will have met similar inclusion criteria to the ones for this study in the past, so we anticipate that most of them will meet inclusion criteria. Subjects in the Test Run will not be required to have shown significant difference in their PK and will be recruited from our general clinic population. However, they may be included in the RCT period provided they meet these recruitment goals.

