V. d. ii. Randomization of Study Visit Order

Once the subject has been enrolled and eligibility of subjects has been established, subjects will be randomized to one of the possible three visit orders. The Test Run period is not randomized; all subjects will only use the insulin-only iLet with BC222 lispro.

V. d. iii. General Study Policies for all Study Arms (including the Test Run):

- Subjects will remain within a geographic boundary established based on 250 miles from the designated base for study personnel at all times and will avoid any air travel.
- If the subject is sleeping at home, the designated contact (or one of the designated contacts, if two individuals are sharing the job) must also be at home. If the subject is traveling within the geographic boundary, the designated contact must go with them.
- Subjects and their designated contact will keep a charged mobile phone on their person (or at their bedside) at all times and will answer calls from the study staff.
- Study subjects will keep a Contour Next One glucometer easily accessible at all times in case a calibration is needed, and they will do all calibrations with this meter. They will keep a glucometer, fast-acting carbohydrates, and a glucagon emergency kit easily accessible at home in case their designated contact needs to use it.
- Subjects should use the study provided Contour Next One glucometer for all BG checks throughout the study. They are encouraged to check their BG at least four times a day, before meals and before bedtime. They will also be encouraged to check before exercise and at intervals during exercise, and for any symptoms of hypoglycemia. There are no restrictions on additional checks and subjects should check as often as they wish to confirm the accuracy of the Dexcom CGM and for safety.
- Subjects will wear leur-lock compatible infusion sets throughout the study.
- Subjects and their designated contact will not use any recreational drugs or drugs of abuse, other than alcohol. The need to take prescription drugs that dull the sensorium, reduce sensitivity to symptoms of hypoglycemia, or hinder appropriate decision-making may be grounds for exclusion from the trial or discontinuation of participation, a decision that will be made by the principal investigator.

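### The three visit orders and their allocation are not specified, so period balance is not guaranteed, and the primary paired tests carry no period term

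*Combined protocol and SAP*

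**What the plan says.** Aim 1 (section II) has up to 30 adults complete "three 7-day study arms using insulin lispro, insulin aspart, and BC222 lispro in the bionic pancreas in random order". Section V.d.ii, on the randomisation itself, says that "subjects will be randomized to one of the possible three visit orders". It does not list the orders, call them a Latin square, or give an allocation ratio, blocking or stratification, and no other section does.

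Section III.c builds the sample from two pharmacokinetic (PK) groups. "We will recruit up to 15 subjects who exhibited an atypical PK profile", it says, and it plans up to 15 more whose lispro and aspart profiles do not differ. Section VI.c hopes to enrol all 22 participants of the earlier PK study.

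For analysis, section VI.b plans three pairwise comparisons of the insulins. The co-primary outcomes are mean CGM glucose and the fraction of time below 54 mg/dl. The paragraph that closes VI.b.3 states: "We will use paired t-test for comparison of means for normally distributed outcomes", with the Wilcoxon signed rank test for outcomes that are not normal. Period enters only in a secondary analysis, where "we will look for any period effect and any interaction between treatment and period".

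**The concern.** A crossover protects its treatment contrasts from period effects in two ways: by balancing treatments over periods, and by fitting period in the analysis. Here the first cannot be confirmed and the second is absent from the primary tests.

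Which three orders are used matters. One way to arrive at three is to keep lispro before aspart and let BC222 lispro go first, middle or last. Any drift over the three weeks would then fall directly into the lispro–aspart contrast. A cyclic square has the same number of orders and no such bias. The text does not let a reader tell the two apart.

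If the orders are balanced, omitting period from the paired tests is a matter of precision only. Each person's difference still contains the gap between the two periods in which that person took the two insulins. That gap averages to zero across people but stays in the error variance.

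**Working it through.** **Inputs.** From the documents: three insulins, each taken once; up to 30 completers; up to 15 per PK group; 22 as the hoped-for recruitment from the earlier study. Assumed, because the documents do not give them: a linear drift d of 0, 2 or 5 mg/dl per period, a paired-difference SD of 8–12 mg/dl, and a true difference of 5 mg/dl for power. There is no power calculation in the plan to reproduce.

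**1. Sets of three orders.** Three insulins have 3! = 6 orders, and there are C(6,3) = 20 sets of three. Write L, A, B for lispro, aspart and BC222 lispro, and number the periods 0, 1, 2. With equal allocation, the bias in L − A is d times the mean over orders of (period of L − period of A).
- Cyclic set LAB, ABL, BLA: (−1 + 2 − 1)/3 = 0, and likewise for the other two contrasts.
- L before A with B moving (LAB, LBA, BLA): (−1 − 2 − 1)/3 = −1.33, a bias of 1.33d in size.

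| Largest pairwise bias | Number of sets |
|---|---|
| 0 | 2 (the two cyclic squares) |
| 0.67d | 12 |
| 1.33d | 6 |

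**2. Allocation within a balanced set.** In a cyclic square the period gap takes the values −1, −1 and 2, with mean 0 and variance (1 + 1 + 4)/3 = 2. All six orders also give variance 2. Under unrestricted randomisation the chance bias therefore has SD d√(2/N):
- N=30: 0.26d
- n=15 (one PK group): 0.37d

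With the cyclic square in blocks of three, the imbalance is 0 whenever n is a multiple of three and 2d/n otherwise: 0.18d at n=11, 0.09d at n=22, 0 at n=15 and n=30.

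**3. Period left in the error.** With balanced orders the variance of the paired difference is SD² + 2d², so the reported standard error is multiplied by √(1 + 2d²/SD²):

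| d (mg/dl) | SD 8 | SD 12 |
|---|---|---|
| 0 | 0% | 0% |
| 2 | √(1 + 8/64) − 1 = 6% | √(1 + 8/144) − 1 = 3% |
| 5 | √(1 + 50/64) − 1 = 33% | √(1 + 50/144) − 1 = 16% |

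Simulated power at N=30 for the assumed 5 mg/dl difference, two-sided 5%:

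| SD | Paired t at d = 0, 2, 5 | Period in the model |
|---|---|---|
| 8 | 91, 89, 75% | 92% |
| 12 | 59, 58, 47% | about 61% |

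The paired t-test rejects a true null about 4–5% of the time at d=2 and 1–2.5% at d=5, so it becomes conservative.

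**4. Degrees of freedom.** At N=30 there are 90 arm means. After 30 participant terms and 2 insulin terms, 58 df remain; 2 period terms leave 56. Of the 4 treatment-by-period df that VI.b plans to examine, three cyclic orders make 2 estimable, and both are aliased with carryover. All six orders make all 4 estimable.

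**The case against.** A reader might infer that three is simply wrong, because three insulins in random order have six orders. The documents do not support that. Random assignment to one of three cyclic sequences is a random order, and with equal allocation it gives the same unbiased contrasts and the same variance as six. Using six is a trade-off. It makes more of the interaction estimable, in an analysis that the plan already concedes is probably underpowered, and it needs more care to stay balanced in groups of 15 or fewer.

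A reader might also infer, from "A final insulin-only bionic pancreas arm will use the experimental ultra-rapid insulin BC222 insulin lispro" in Aim 1, that BC222 lispro always comes last. Aim 1 itself puts all three insulins in random order, and the word most naturally marks the last item in a list. No finding rests on it.

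Nor can it be said that the paired tests are invalid. With balanced orders they are unbiased and at worst conservative. With unrestricted allocation over a balanced set, the 2d² in their error is the same quantity that produces the chance bias.

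The strongest objection concerns size. At d=2 the loss is slight. At d=5 the shift from first to third week is 10 mg/dl, as large as the between-person SD of 10 mg/dl that VI.c reports for mean glucose on the bionic pancreas. Automated control, re-initialisation of the device at each arm (V.d.v) and the request for similar diet and exercise (V.d.iii) all argue against drift that large. VI.c also calls the study exploratory. This objection stands as to weight. It does not supply the missing orders, and an exploratory aim excuses the absence of a power calculation more readily than an undefined randomisation.

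**Conclusion.** The point holds as a gap in design specification together with a modest inefficiency in the primary analysis. Whether the group contrasts are protected against period effects depends on orders and an allocation that the plan does not state. The possible bias runs from 0, for either cyclic square with equal allocation, to 1.33d for the worst three-order sets. Omitting the period term costs nothing if there is no drift, little at 2 mg/dl per period, and a material share of power only at about 5 mg/dl per period. All mg/dl, percentage and power figures rest on assumed drift and SD; the multiples of d assume only that drift is linear. The case for change is that the remedy is nearly free, not that harm has been shown.

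Period adjustment should not be read as rescuing the single-participant comparisons in VI.b and VI.c. Each person takes each insulin in one period only, so insulin and period stay confounded within that person under any set of orders.

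**What to change.** 1. **V.d.ii.** List a period-balanced set of orders. A cyclic three-order Latin square is enough. Allocate equally in small permuted blocks within each PK group (blocks of three for the cyclic square), so that balance holds if a group stops short of 15. All six orders is an option if the treatment-by-period analysis matters; alternating the two cyclic squares in blocks of three keeps every block balanced.
2. **VI.b, mean CGM glucose.** Make the primary group analysis a mixed model with insulin and period as fixed effects and participant as random. Keep the paired t-test as a sensitivity analysis.
3. **VI.b, time below 54 mg/dl.** Use a period-adjusted analysis here too, for example the same model on a transformed scale or a period-adjusted rank test, with Wilcoxon as a sensitivity analysis.
4. **VI.b and VI.c.** State that period adjustment applies to the group contrasts and does not remove insulin–period confounding from the single-participant comparisons.

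The cost is 2 df (58 to 56 at N=30), a blocked randomisation list stratified by PK group, and a few lines of SAP text. No participants or visits are added.
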